5.2 Description of MPDL3280A

The MPDL3280A drug product is provided in a single-use, 20-cc USP/Ph. Eur. Type 1 glass vial as a colorless-to-slightly yellow, sterile, preservative-free clear liquid solution intended for IV administration. The vial is designed to deliver 20 mL (1200 mg) of MPDL3280A solution but may contain more than the stated volume to enable delivery of the entire 20 mL volume. The MPDL3280A drug product is formulated as 60 mg/mL MPDL3280A in 20 mM histidine acetate, 120 mM sucrose, 0.04% polysorbate 20, pH 5.8.

MPDL3280A must be refrigerated at 2°C-8°C (36°F-46°F) upon receipt until use. MPDL3280A vials should not be used beyond the expiration date provided by the manufacturer. No preservative is used in the MPDL3280A drug product; therefore, each vial is intended for single use only. Vial contents should not be frozen or shaken and should be protected from direct sunlight.

For further details, see the MPDL3280A IB.

5.3 Preparation and Administration of Study Treatment

Rociletinib is available as 125 or 250 mg tablets. Patients will self-administer oral rociletinib BID at the cohort-assigned dose throughout the treatment period, unless dose reduction is required for adverse event management. Patients should take rociletinib as directed by the treating physician. Patients will be instructed to take each dose of rociletinib with 8 oz. (240 mL) of water and with a meal or within 30 minutes after a meal. (During the PK visit on C1D8 [Phase 1 only], patients will be more specifically guided to take the morning dose of rociletinib within 30 minutes after the start of the meal.) Tablets should be swallowed whole. Missed doses (ie, patient does not take dose within 6 hours of the scheduled time) or vomited doses will not be made up, and the patient should resume rociletinib dosing with the next scheduled dose.

The Investigator or designee will be responsible for distributing the appropriate strength(s) of PO rociletinib tablets to all patients. A sufficient number of tablets will be provided to the patient to last until the next scheduled visit. Patients will be instructed to record daily doses taken or not taken on a patient diary, and will be instructed to bring their rociletinib tablets and diary to the next scheduled visit for reconciliation by site personnel.

On PK sampling days, patients will be instructed to not administer study drug at home, but to bring rociletinib and their dosing diaries to the clinic along with breakfast. Patients will be instructed when to take their doses of rociletinib in the clinic and when to have their meal, in the context of the PK schedule and/or MPDL3280A dose administration for the given visit (see Table 2).

The only dose of MPDL3280A for all patients in this study is a fixed dose of 1200 mg administered by IV infusion on the first day of each protocol-specified 21-day treatment cycle (see Table 1). MPDL3280A will be delivered in infusion bags with IV infusion lines, product-contacting surfaces of polyvinylchloride (PVC) and polyolefin, and 0.2 µm in-line filters (filter membrane of polyethersulfone). No incompatibilities have been observed between MPDL3280A and PVC or polyolefin infusion materials (bags and infusion lines). Administration of MPDL3280A will be performed in a setting with emergency medical facilities and staff who are trained to monitor for and respond to medical emergencies.

The initial dose of MPDL3280A will be delivered over 60 (\pm 15) minutes. If the first infusion is tolerated without infusion-associated AEs, the second infusion may be delivered over 30 (\pm 10) minutes. If the 30-minute infusion is well tolerated, all subsequent infusions may be delivered over 30 (\pm 10) minutes. For the first infusion, the patient's vital signs (heart rate, respiratory rate, blood pressure, and temperature) should be determined within 60 minutes before the infusion, every 15 [\pm 5] minutes during the infusion, and 30 (\pm 10) minutes and 2 hours (\pm 15 minutes) after completion of the infusion. For subsequent infusions, vital signs will be collected within 60 minutes before the infusion, during the infusion as clinically indicated or if symptoms occurred in the prior infusion, and 1 hour (\pm 10 minutes) after the infusion.

No premedication will be allowed for the first dose of MPDL3280A. Premedication may be administered for subsequent infusions at the discretion of the treating physician after consultation with the Medical Monitor.

5.4 Blinding/Masking of Treatment

This is an open-label study; the investigational product will not be blinded or masked. All patients enrolled will receive PO rociletinib and IV MPDL3280A.

5.5 Treatment Compliance

Documentation of dosing will be recorded in a study-specific diary card provided by the Sponsor (or designee). Study site personnel will enter the scheduled daily doses of rociletinib and the number of tablets to be taken each day. Patients (or legally authorized representative) will be asked to record dosing information for PO rociletinib taken at home in the diary card and to bring the diary card and all unused tablets with them to scheduled clinic visits. Study site personnel will review the dosing information with the patient (or legally authorized representative) on scheduled clinic visit days and complete a compliance check and tablet count. Study site personnel will record compliance information on the eCRF and retain the diary card in the patient's medical record.

5.6 Study Drug Accountability

All investigational medicinal products (IMPs) required for completion of this study (rociletinib, MPDL3280A) will be provided by the Sponsor. Study personnel will maintain accurate records of rociletinib and MPDL3280A shipments/receipts, administration, and drug reconciliation. The investigational site will acknowledge receipt of IMPs, using the IxRS to confirm the shipment condition and content. The study site is responsible for the return or destruction of rociletinib and MPDL3280A as required. A drug management system will manage rociletinib and MPDL3280A inventory at all sites. The system will be required to manage study treatment requests and shipments.

Any rociletinib and/or MPDL3280A accidentally or deliberately destroyed must be accounted for. All bottles or vials must be accounted for before their destruction at the study center. Unused bottles or vials should be destroyed locally. If destruction at the site is not possible, supply should be returned to the drug depot. During the course of the study and at completion of the study, the number of bottles and vials shipped, destroyed, and returned must be reconciled.

Accurate records of all IMPs received at, dispensed from, returned to, and disposed of by the study site should be recorded on the Drug Inventory Log.

5.7 Dose Modification Guidelines

5.7.1 Study Treatment Dose Reductions

5.7.1.1 Rociletinib Dose Reductions

From a starting dose of 500 mg BID rociletinib, up to two dose reductions are available (Table 7). No dose reduction below 250 mg is permitted. All dose reductions are permanent.

Current Dosage	Dose Reduction
500 mg PO BID	375 mg PO BID
375 mg PO BID	250 mg PO BID
250 mg PO BID	No further dose reduction allowed

Table 7:Dose Reductions for Rociletinib

BID, twice daily; PO, oral.

5.7.1.2 MPDL3280A Dose Reductions

The only dose of MPDL3280A available on this study is 1200 mg. Dose reductions are not permitted.

5.7.2 Phase 1 – Run-in-Period

Rociletinib monotherapy will be administered orally BID during the 7-day Run-in-Period. Dose reductions of rociletinib during the Run-in-Period are not allowed for reasons other than a DLT. Dose delays of rociletinib for up to 48 hours for toxicity management is allowed. Any patient who experiences an AE(s) that requires either a delay of treatment for more than a total of 48 hours or a dose reduction during the 7-day Run-in Period of rociletinib monotherapy will not be eligible for combination therapy. Such a patient will only receive monotherapy rociletinib for the duration of participation in the study.

5.7.3 Phase 1 – Cycle 1

The first dose of MPDL3280A at 1200 mg will be administered by IV on C1D1. Dose reductions of rociletinib are not allowed for reasons other than a DLT or a decision by the CSC based on emerging safety data. Dose delays of rociletinib are not allowed for reasons other than toxicity. Patients are eligible for safety and DLT evaluation of the cohort if they receive at least 75% of the planned total dose of each study drug within Cycle 1 or they experience a DLT at any time during Cycle 1.

5.7.4 Beyond DLT Assessment (Phase 1 – Cycle 2+ and Phase 2 – All Cycles)

For patients who experience a toxicity that is equivalent to a DLT – If the toxicity is assessed as being related to rociletinib, the next dose of rociletinib should be held until resolution of the toxicity to Grade 1 or to the baseline level (if severity > Grade 1 at baseline) and then reduced to the next dose level of rociletinib (Table 7), unless permanent discontinuation of rociletinib is required per toxicity management guidelines of the protocol (Sections 6.1 and 6.3). If the toxicity is assessed as being related to MPDL3280A, the next dose of MPDL3280A should be held until the toxicity has resolved to Grade 1 or to the baseline level (if severity > Grade 1 at baseline), unless permanent discontinuation of MPDL3280A is required per toxicity management guidelines of the protocol (Sections 6.2 and 6.3). In addition, because there is no available antidote for MPDL3280A and discontinuation of MPDL3280A may not have immediate therapeutic effect, consideration may be given to holding rociletinib doses temporarily even if the toxicity is not attributed to rociletinib.

Dose holds for toxicity or for reasons unrelated to toxicity (eg, elective surgery or intercurrent illness) are allowed for up to 14 days for rociletinib and for up to 42 days (2 cycles) for MPDL3280A. Permission for a longer dose hold must be granted by the Sponsor's Medical Monitor; in the absence of such permission, the patient should permanently discontinue all study treatment (Section 11.1).

Intra-Subject Dose Escalation: For patients in the Dose Finding Phase (Phase 1) who have completed 2 cycles of therapy at their original assigned dose with no DLTs, intra-subject dose escalation to a higher dose level of rociletinib (if applicable) may be permitted with approval from the Sponsor's Medical Monitor after consideration of cumulative safety data and provided that the dose level to which the patient will escalate has already been evaluated and has a DLT rate < 33%. Intra-subject dose escalation will begin at the start of a dosing cycle at the Investigator's discretion and requires prior approval by the Sponsor's Medical Monitor. For patients in the Dose Expansion Phase (Phase 2), no intra-subject dose escalation is allowed.

In cases where a patient must discontinue rociletinib or MPDL3280A for toxicity, monotherapy with the other agent may be continued until the patient meets any of the criteria for permanent treatment discontinuation (see Section 11).

A summary of dose modification allowances is shown in Table 8.

	Dose Finding Phase (Phase 1)			Phase 1 and Phase 2		
	Run-In	Cycle 1		Cycle 2+		
	Rociletinib	Rociletinib	MPDL3280A	Rociletinib	MPDL3280A	
Dose Reduction ^a	Not allowed unless due to DLT ^b	Not allowed unless due to DLT or CSC decision	Not allowed	Allowed for toxicity (see Table 7 for dose reductions)	Not allowed	
Dose Hold	Allowed up to 48 hours for toxicity management ^b	Allowed for toxicity; must receive >75% doses to be evaluable for DLT	Not allowed	Allowed up to 14 days ^c for toxicity or reasons unrelated to toxicity	Allowed up to 42 days ^c for toxicity or reasons unrelated to toxicity	

Table 8: Phase 1 and Phase 2 Dose Modification

CSC, Clinical Safety Committee; DLT, dose-limiting toxicity.

^a Dose reductions are permanent.

^b If dose reduction or more than 48-hour delay of rociletinib dosing is required in Run-in-Period, patient will not be eligible for combination therapy but rather will continue rociletinib monotherapy.

^c If a longer hold is needed for slowly resolving toxicity, Sponsor approval is required. If either study drug must be discontinued for toxicity, monotherapy with the other study drug may be continued.

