3.2.1 Dose-Limiting Toxicity

Determination of DLTs will be made during the first 21 days of combination treatment with rociletinib and MPDL3280A (ie, during Cycle 1 after the rociletinib Run-in-Period) in the Dose Finding Phase. A DLT is defined as a clinically significant AE or laboratory abnormality assessed as at least related to the study drug (rociletinib and/or MPDL3280A), unrelated to disease progression, and that meets any of the following criteria:

Cytopenia:

- Grade 4 neutropenia persisting for more than 7 days;
- Febrile neutropenia, defined as an absolute neutrophil count (ANC) < 1000/mm³ and a single temperature of > 38.3°C (101°F);
- Grade 4 thrombocytopenia persisting for more than 7 days or thrombocytopenia with clinically significant bleeding (ie, bleeding that requires blood or platelet transfusion or other medical intervention, or that may cause disability or death, such as cerebral hemorrhage).

Organ Toxicity:

• Grade \geq 3 symptomatic hepatic toxicities lasting for > 48 hours, or Grade \geq 3 asymptomatic hepatic toxicities lasting for > 7 days with the following exception:

- For patients with Grade 2 Alkaline phosphatase (ALP) abnormality at baseline, an increase to > 8 × the upper limit of normal (ULN) lasting > 48 hours (if symptomatic) or > 7 days (if asymptomatic) will be considered a DLT.
- Grade \geq 3 nonhematologic, nonhepatic organ toxicity, with the following exceptions:
 - **DLT Toxicity Exceptions**
 - Grade 3 nausea, vomiting, or diarrhea that resolves to Grade ≤ 1 within 7 days after starting appropriate supportive therapy (see Section 6.2.2);
 - Grade ≥ 3 asymptomatic or mildly symptomatic rash that can be adequately managed with supportive care (see Section 6.2.4) or symptomatic rash that resolves to become asymptomatic and/or Grade ≤ 2 within 7 days of appropriate supportive therapy;
 - Grade \geq 3 fatigue that resolves to Grade \leq 2 within 7 days;
 - Grade 3 arthralgia that can be adequately managed with supportive care or that resolves to Grade ≤ 2 within 7 days;
 - Grade 3 autoimmune thyroiditis or other endocrine abnormality that can be managed by endocrine therapy and that would not necessitate initiation of systemic corticosteroids;
 - Grade 3 fever (in the absence of any clinically significant source of fever) that resolves to Grade ≤ 2 within 7 days with supportive care;
 - Grade 3 laboratory abnormality that is asymptomatic and deemed by the Investigator to be not clinically significant;

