At each dose level, after the first evaluable 3 patients have completed Cycle 1, the CSC will meet to evaluate the Dosing Cohort data and to make a decision on the next step for Dosing Cohort assignment (increase dose, decrease dose, maintain same dose, or stop), which will be guided by the mTPI decision table (Appendix H). A patient will be deemed evaluable for safety and DLT determination if they have received at least 75% of the planned total dose of each drug within Cycle 1. Patients who receive <75% of the planned total dose of either rociletinib or MPDL3280A for reasons other than study drug-related AEs will not be included in the evaluation of the Dosing Cohort and will be replaced. If the dose is maintained, up to an additional 6 patients may be enrolled at the same dose, and the next safety evaluation will take place after all patients have completed Cycle 1. The CSC may decide to meet at any time to evaluate a Dosing Cohort if a safety signal arises or other data become available to justify re-evaluation of the Dosing Cohort before it is fully enrolled.

The enrollment/evaluation process will continue until at least 6 patients have been treated at any single dose level or enrollment of the maximum sample size of 18 patients for the Phase 1 portion of this study has been achieved.

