6.3 Overlapping Expected or Potential Toxicities

Guidelines for the management of specific expected or potential overlapping toxicities for rociletinib and MPDL3280A are described in Table 18.

Table 18:Management of Overlapping Toxicities

Toxicity	Attribution to both agents
Rash/Skin Toxicity:	Grade 2: continue both agents; initiate supportive care.
	Grade 3:
	 Obtain dermatology consult;
	■ Hold rociletinib and MPDL3280A until resolved to ≤ Grade 1, then reinitiate rociletinib at a dose agreed upon with the Sponsor's Medical Monitor; (dose delays longer than 14 days also require discussion with the Medical Monitor);
	 Restart MPDL3280A if rash does not occur within 14 days of rociletinib re-initiation;
	 Hold rociletinib and permanently discontinue MPDL3280A if the patient experiences recurrent Grade ≥ 3 skin toxicity. When rash is Grade 1, restart rociletinib at previous dose. If Grade ≥ 3 rash recurs, rociletinib should be discontinued permanently.
	Grade 4 : Permanently discontinue MPDL3280A. Hold rociletinib until rash is Grade 1 and restart at one dose level lower (dose delays longer than 14 days require discussion with the Medical Monitor). If Grade \geq 3 rash recurs, rociletinib should
	be discontinued.
Diarrhea:	Grade 2 : Supportive care unless > 48 to 72 hrs. Then reduce dose of rociletinib and hold MPDL3280A until resolves to < Grade 1.
	Grade 3 : Hold rociletinib and MPDL3280A Obtain gastroenterology consult, discontinue NSAIDs or medications known to exacerbate colitis, Initiate steroid treatment. If resolves to < Grade 1, then restart rociletinib at next lower dose. If no recurrent symptoms, within 14 days resume MPDL3280A as long as steroid dose is ≤ 10 mg oral prednisone equivalent per day (dose delays longer than 14 days require discussion with the Medical Monitor).
	Grade 4 : MPDL3280A should be permanently discontinued. Hold rociletinib until diarrhea is Grade 1 and restart at one dose level lower. If Grade \geq 3 diarrhea recurs, rociletinib should be permanently discontinued (dose delays longer than 14 days require discussion with the Medical Monitor).
Nausea/Vomiting:	Grade1-2: Continue treatment. Begin maximum supportive care and adequate anti-emetic treatments (see Section 7.6.1 for guidance on avoiding QT-prolonging concomitant medication).
	Grade ≥ 3:

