	 Begin/continue maximum supportive care and adequate combination anti-emetic treatments (see Section 7.6.1 for guidance on avoiding QT-prolonging concomitant medication). Consider gastroenterology consult;
	 Hold both rociletinib and MPDL3280A until < Grade 1. Restart rociletinib at next lower dose. If no recurrent symptoms, restart MPDL3280A;
	• If Grade \geq 3 nausea/vomiting recurs, MPDL3280A should be discontinued.

Toxicity	Attribution to both agents
Ocular Toxicity:	Grade ≥ 2:
	 Hold both study drugs until < Grade 1 (dose delays longer than 14 days require discussion with the Medical Monitor);
	 Obtain ophthalmology consult; uveitis or episcleritis may be treated with topical corticosteroid eye drops;
	 Reintroduce rociletinib at a reduced dose when symptoms resolved to Grade ≤ 1. If no recurrent symptoms, restart MPDL3280A; MPDL3280A should be permanently discontinued for immune-mediated ocular disease that is unresponsive to local immunosuppressive therapy.
Laboratory abnormalities	Grade \geq 3 Laboratory abnormalities related to study drug that are asymptomatic and deemed by the Investigator not to be clinically significant
	 After discussion between Investigator and Medical Monitor, rociletinib dosing may be delayed, and treatment subsequently resumed at the current dose level or at a reduced dose. If abnormality persists > 7 days, MPDL3280A dosing may also be held and subsequently resumed at the same dose level when toxicity resolves to baseline grade plus one.
Liver toxicities	Grade \geq 3 AST, ALT, or bilirubin abnormalities (or AST or ALT \geq 10 × ULN in patients with hepatic metastases) related to study drug that are asymptomatic and deemed by the Investigator not to be clinically significant
	• Hold both study drugs until recovery Grade ≤ 1 ;
	 Initiate systemic steroids IV for 48 hours followed by oral taper;
	 Monitor LFTs QOD until decreasing, then weekly;
	 If resolved to baseline grade plus one (eg, if baseline Grade 1, then Grade 2) resume MPDL3280A dosing;
	 If AE persists permanently discontinue MPDL3280A.
Other Grade ≥ 3 non-hematologic or Grade 4	 Hold rociletinib and MPDL3280A until recovery to Grade ≤ 1 and then restart rociletinib at a reduced dose and MPDL3280A at the same dose.
hematologic toxicity	 If the Grade 4 AE recurs (a second time), then MPDL3280A should be discontinued.
	 If the Grade 4 AE recurs (a third time), then rociletinib should be discontinued.

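### Phase 1 Cycle 1: the rule limiting rociletinib reductions conflicts with Table 18, and a patient reduced without a DLT can be counted as DLT-free at the higher dose

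*Combined protocol and SAP*

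**What the plan says.** **Reduction rules.** For Phase 1 Cycle 1, Section 5.7.3 states that dose reductions "of rociletinib are not allowed for reasons other than a DLT or a decision by the CSC based on emerging safety data". Table 8 repeats this. For the run-in, Section 5.7.2 states: "Dose reductions of rociletinib during the Run-in-Period are not allowed for reasons other than a DLT". Table 8 repeats that too.

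**When a DLT can occur.** Section 3.2.1: "Determination of DLTs will be made during the first 21 days of combination treatment with rociletinib and MPDL3280A", that is, "during Cycle 1 after the rociletinib Run-in-Period". For non-hematologic, non-hepatic toxicity a DLT must be Grade 3 or higher. Grade 3 nausea, vomiting or diarrhea that settles to Grade 1 or less within 7 days of supportive therapy is exempt.

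**Table 18 (Section 6.3), for events attributed to both agents.**
- Grade 2 diarrhea: "Supportive care unless > 48 to 72 hrs. Then reduce dose of rociletinib and hold MPDL3280A".
- Ocular toxicity of Grade 2 or higher: both drugs are held, then "Reintroduce rociletinib at a reduced dose when symptoms resolved to Grade ≤ 1".
- Nausea or vomiting of Grade 3 or higher: both drugs are held, and rociletinib is restarted one level down.

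**Evaluability.** Under Section 3.2.2 a patient is evaluable "if they have received at least 75% of the planned total dose of each drug within Cycle 1". Section 5.7.3 uses the same threshold and adds patients who have a DLT. Table 8 instead requires more than 75%. Table 7 takes 500 mg BID down to 375 mg BID, which is also the Cohort -1 dose in Table 5.

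**The concern.** The mTPI tally at 500 mg BID is meant to describe tolerability at 500 mg BID. Section 5.7.3 and Table 8 protect that by barring Cycle 1 reductions that are not tied to a DLT or a CSC decision. Table 18 tells sites to reduce for events that Section 3.2.1 does not count as DLTs. A site that follows Table 18 creates a patient who took the lower cohort's dose for part of the cycle, did so because of toxicity, and still enters the table as a non-event at the higher dose. No rule flags or separates such a patient. With cohorts of three to nine, one patient can change the decision, and the dose chosen then goes to up to 75 Phase 2 patients without a run-in.

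The run-in rule has its own fault: the only reason it allows for a reduction cannot arise before combination treatment starts.

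**Working it through.** **1. Do the Cycle 1 texts conflict?**

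| Event attributed to both agents | DLT under 3.2.1? | Reduction under 5.7.3 and Table 8 | Table 18 |
|---|---|---|---|
| Grade 2 diarrhea beyond 48 to 72 h | No (below Grade 3) | Barred unless the CSC decides | Reduce |
| Grade 2 ocular toxicity | No (below Grade 3) | Barred unless the CSC decides | Hold, then restart reduced |
| Grade 3 nausea or vomiting resolving within 7 days | No (exempt) | Barred unless the CSC decides | Hold, then restart one level down |

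No sentence gives precedence. Section 6 is not confined to later cycles: the DLT exceptions in Section 3.2.1 themselves cite Sections 6.2.2 and 6.2.4 for supportive care.

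**2. Does a reduced patient stay evaluable?** Cohort 1 is 500 mg BID for 21 days. With reduction from Day k and no held doses, the share of planned dose is

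[(k − 1) × 500 + (22 − k) × 375] / (21 × 500)

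- Day 4: (1500 + 6750) / 10500 = 78.6%
- Day 8: (3500 + 5250) / 10500 = 83.3%
- Day 15: (7000 + 2625) / 10500 = 91.7%

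The Grade 2 diarrhea row reduces rociletinib without holding it, so these figures apply to it directly. MPDL3280A is given once in the cycle, on Day 1, so its own 75% is already met.

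With F full-dose days and h held days, the bar is 500F + 375(21 − F − h) ≥ 0.75 × 21 × 500 = 7875. Since 375 × 21 = 7875, this reduces to F ≥ 3h. A 1-day hold needs 3 full-dose days, a 2-day hold 6, a 3-day hold 9. Because F + h cannot exceed 21, a hold of more than 5 days always falls short. The ocular and nausea/vomiting rows therefore keep some patients evaluable and not others.

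For Cohort -1 (375 to 250 mg BID, no hold), 375F + 250(21 − F) ≥ 0.75 × 21 × 375 gives F ≥ 656.25 / 125 = 5.25 days.

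**3. Is the bar itself consistent?** 375/500 is exactly 75%. The two wordings differ exactly there, and whenever F = 3h. Section 3.2.2 also replaces patients below 75% only when the cause is not a drug-related AE. Read literally, an AE-driven shortfall without a DLT is neither evaluable nor replaced.

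**4. Can one such patient change a decision?** The Appendix H table was rebuilt first: Beta(1,1) prior, posterior probability divided by interval width for (0, 0.28), (0.28, 0.38) and (0.38, 1), and U if P(p > 0.33) > 0.95. All 91 cells in the rows for 0 to 7 DLTs match the printed table. As an example:

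- 2/3, Beta(3,2): E 0.0694/0.28 = 0.248; S 0.0876/0.10 = 0.876; D 0.8431/0.62 = 1.360. Decision D.
- 2/4, Beta(3,3): E 0.1376/0.28 = 0.492; S 0.1458/0.10 = 1.458; D 0.7165/0.62 = 1.156. Decision S.

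| Reduced patient left out | Reduced patient counted as no DLT |
|---|---|
| 2/3: D | 2/4: S |
| 3/5: D | 3/6: S |
| 1/5: S | 1/6: E |

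The third line matters less, because 500 mg BID is the highest planned cohort.

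**5. Run-in.** Sections 3.2 and 5.7.2 bar a patient reduced in the run-in from combination treatment, and Section 3.2 replaces that patient. The contribution to the mTPI numerator and denominator is zero.

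**The case against.** The best defence is that Section 5.7.3 is the specific rule for Phase 1 Cycle 1. Section 6 describes itself as guidance and sends dose modification back to Section 5.7. Within Section 5.7, the toxicity tables are invoked from Section 5.7.4, which covers the time after DLT assessment. That is a reasonable reading, but the documents do not state it and Table 18 carries no such limit. Even if it is accepted, a CSC-ordered reduction without a DLT remains permitted and leads to the same count.

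A second defence is that the 75% bar is a deliberate tolerance for partial exposure. It is, and counting such patients at the assigned dose is a choice the sponsor may defend. But the bar does not distinguish missed doses from a toxicity-driven move to the next cohort's dose, and the plan does not say that this was intended.

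Third, a reader might infer that sites are forced to keep a patient on a dose that Table 18 says to lower. The documents do not support that: rociletinib may be held for toxicity in Cycle 1, the CSC may authorize a reduction, and it may meet at any time. This objection stands.

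Fourth, a reader might infer that the recommended dose is biased upward. That is not shown. The CSC sets it on cumulative safety, tolerability and PK data, not on the table alone.

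**Conclusion.** The contradiction is real. For Phase 1 Cycle 1, Section 5.7.3 and Table 8 cannot be reconciled with Table 18 as written for the three kinds of event listed. The consequence for the tally is confirmed for patients reduced with no hold or a short one: at 78.6% (Day 4) or 83.3% (Day 8) of planned dose they are evaluable, and one of them can change D to S. This assumes that a site applies Table 18 in Cycle 1 or that the CSC orders a reduction without a DLT. The comparison is with leaving the patient out; if the patient were replaced, the result would depend on the replacement (3/6 gives S, 4/6 gives DU).

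Three stronger readings do not hold:
- That run-in reductions contaminate the count. Those patients never enter it, so the run-in fault is one of wording only.
- That every reduced patient counts, even one on 375 mg BID for the whole cycle. Reduction from Day 1 gives exactly 75.0%, but the cited rows cannot produce it: the event must be attributed to both agents, MPDL3280A starts on Day 1, diarrhea must first persist, and the other rows require a hold. Table 8's stricter threshold would also exclude it.
- That the shift from 0/3 to 1/3 to 2/3 measures the effect. That shift recodes a patient as a DLT, which is a different question from whether to include the patient.

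**What to change.** Reconcile Sections 3.2.1, 3.2.2, 5.7.2 and 5.7.3 and Table 8 with Table 18 for the Phase 1 run-in and Cycle 1, and state which text governs. Reword the run-in condition so that it does not depend on an event that Section 3.2.1 places after the run-in. Use one evaluability threshold throughout, and say how a patient below it because of a drug-related AE without a DLT is handled. Prespecify how a Cycle 1 patient reduced without a DLT enters the mTPI tally, and show the CSC the dose each patient actually took. Whether such patients are left out, replaced or counted with a flag is a design choice; it should be made before the first cohort review. No dose or clinical rule is proposed here. The cost is amendment wording and possibly one replaced patient in a cohort.
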